2 INTRODUCTION

2.1 STUDY RATIONALE

This work will result in a new approach to extend the efficacy of supervised training beyond brief periods of direct exposure and prolong engagement in positive behaviors after program completion.

2.2 BACKGROUND

Supervised exercise with a trained instructor^{3,4} is most effective in maximizing health benefits, is popular among adults>60y, and is most common in aging research.⁵⁻¹⁰ Supervision results in higher training effects and program adherence^{7,8,11,12} due to personal attention and interaction with the trainer that motivate participants.^{8,11} Drawbacks of the model include a low frequency of trainer contact (60 min, ~1 to 3 times/week) and ineffectiveness in changing behavior outside weekly sessions.⁸ Additionally, adults>60y compensate for increased exercise by increasing sedentary behavior outside training sessions, which attenuates positive gains in health from supervised exercise.^{10,13-19} Independent of physical activity, reducing sedentary time improves cardiometabolic and functional health in adults>60y.^{20,21} Thus, federal guidelines recommend that older adults move more and sit less during the day.²² Strategies to motivate adults>60y who participate in supervised programs to be more active and sit less outside structured weekly training sessions are necessary.

Technologies including wearables and smartphones have great potential to promote daily positive behaviors in adults>60y.²³ Nonetheless, a significant research gap is that “such technologies rarely integrate meaningful two-way communication²⁴” which allows an interventionist to successfully engage an adult via an intelligent, context-sensitive dialogue to problem-solve and motivate change.²⁴ Available two-way communication interventions (e.g., text message and internet-based strategies) have limited meaningfulness due to an inability to appropriately time the communication and tailor it based on ongoing or recent behavior.

Awareness of: (i) ongoing or recent behavior (from sensors), (ii) situational contexts of the behavior, (iii) past conversation, and (iv) the adult’s preferences (# ii, iii, and iv gathered via two-way communication) will help in generating meaningful discourse that allows the creation of an adaptive intervention at a level that was not previously possible. We have integrated wearable sensors with the smartphone to develop a behavior-aware, virtual “Companion” that uses a “human-in-the-loop” approach to enable meaningful two-way communication. Companion builds rich models of typical behavior using sensors and context sensitive ecological momentary assessment (CS-EMA) to deliver intervention components and behavior change strategies using socially engaging, contextually salient, and tailored text-message conversations in near-real-time.

In our feasibility testing (3 m) of Companion, adults>60y (n=6) reduced daily sitting by ~2.1 h and improved health.²⁵ Independent of disease, an active lifestyle also improves cognition in older adults.^{26,27} Thus, an investigation of the impact of Companion on behavioral, cognitive, and physiological outcomes is required.

2.3 RISK/BENEFIT ASSESSMENT

2.3.1 KNOWN POTENTIAL RISKS

There is a risk of physical injury during exercise, particularly if participants have little to no previous experience. Fatigue and muscle soreness may also occur in participants who do not normally engage in physical activity. Exercise is associated with a very small risk of serious medical complications including heart attack and sudden death, although this risk is particularly small in healthy older adults.

There is a potential risk of breach of confidentiality that is inherent in all research protocols.

Some inconvenience and or anxiety may occur due to time required to complete formal rating scales and questionnaires. The cognitive assessments impose some risk of emotional discomfort. Fatigue associated with performing the cognitive tasks- These items will be scored within 24 hours of completion by the subject.

Participants may experience red skin or discomfort from wearing body-worn sensor devices for an extended period of time.

2.3.2 KNOWN POTENTIAL BENEFITS

Increasing physical activity, regular structured exercise, and reduced sedentary behavior, improves cognitive and physiological health.¹⁻³ Supervised exercise programs (group/individual) involving direct contact with a trainer are most effective in maximizing health benefits in adults >60 y; hence, such programs are popular in adults >60 y and are widely offered by aging-related interest groups.^{2,4-8} Supervision results in fewer injuries, higher training effects, and program adherence.^{5,6,9,10} Adherence is due to personal attention and interaction between the participant and supervisor during sessions, which motivate the participant.^{6,9} mHealth technologies including mobile phones and wearables hold immense potential to engage adults >60 y and promote positive behavior change throughout the day.²¹

2.3.3 ASSESSMENT OF POTENTIAL RISKS AND BENEFITS

The risks are minimal and outweighed by the potential benefits to individuals and society
All experimenters involved in the project will be CPR certified.

3 OBJECTIVES AND ENDPOINTS

OBJECTIVES	ENDPOINTS	JUSTIFICATION FOR ENDPOINTS
Primary		
Determine if Companion improves free-living activity and sedentary behavior and	Daily total and bouts of physical	These physical behaviors are directly impacted by motivation communication

OBJECTIVES	ENDPOINTS	JUSTIFICATION FOR ENDPOINTS
sustains this change in adults >60y.	activity and sedentary time.	aimed at promoting positive behavior change.
Tertiary/Exploratory		
(1) Explore if supplementing supervised exercise with Companion further improves and sustains cardiometabolic health, body composition, physical function, muscular and aerobic fitness, and cognition. (2) Examine factors that mediate and moderate change in physical activity and sedentary behavior.	Cardiometabolic health (Plasma glucose, HbA1C, insulin, and lipids; lean and fat mass; Physical function; Cognition; Perceptions of competence related to health behaviors; Autonomy support (from companion); Autonomous motivation (for physical activity); Relatedness (to the Companion); General satisfaction.	These outcomes may be impacted by change in behavior and communication with Companion

4 STUDY DESIGN

4.1 OVERALL DESIGN

Hypothesis (Aim 1): The treatment group will show greater improvements in daily activity and sedentary behavior outcomes than controls after 16 and 24 weeks.

Hypothesis (Aim 2): The treatment group will show greater improvements in health and psychosocial outcomes than controls after 16 and 24 weeks.

Phase: 1A.

Design: Randomized control trial

Participant assignment: 1:1 Simple Randomization conducted by graduate assistant

Number of study group: 2 (control/treatment); intervention period= 4 months; follow-ups after 4 and 6 months.

Number of sites= Single site trial.

Name and description of intervention: Companion; An integrated system of wearable sensors and the smartphone. It is a behavior-aware, virtual “Companion” that uses a “human-in-the-loop” approach to enable meaningful two-way communication. Companion builds rich models of typical behavior using sensors and context sensitive ecological momentary assessment (CS-EMA) to deliver intervention components and behavior change strategies using socially engaging, contextually salient, and tailored text-message conversations in near-real-time.

Description of control group: This group will not receive the Companion, which will be the only difference with the treatment group. I.e., the control group will receive standard treatment– the supervised training program and an exercise prescription for those days without supervision.

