Description of Study	The study intervention consists of wearable sensors integrated with the smartphone to develop a behavior-aware, virtual “Companion” that uses a “human-in-the-loop” approach to enable meaningful two-way communication. Companion builds rich models of typical behavior using sensors and context sensitive ecological momentary assessment (CS-EMA) to deliver intervention components and behavior change strategies using socially engaging, contextually salient, and tailored text-message conversations in near-real-time. The duration of the intervention is 4 months.
Study Duration :	Estimated time (in months) from when the study opens to enrollment until completion of data collection is 6.5 months.
Participant Duration:	Time for each individual participant to complete all study-related tasks is 6.5 months.

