4.2 SCIENTIFIC RATIONALE FOR STUDY DESIGN

An RCT design where the control group does not receive the Companion intervention will enable to tease apart the efficacy of the Companion. The design will minimize the risk of confounding and help to increase confidence in the findings, and thus, are more likely to be representative of the true effect of the intervention.

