4.3 JUSTIFICATION FOR INTERVENTION

The intervention is delivered via text messaging as it is an mHealth intervention that targets behavior improvement when participants are on their own. Participants will receive 4-7 messages from the Companion in intervals of 1-4 hours each day. This limited interval will retain the novelty of the communication and thus interest of the participant in engaging in the study while yielding evaluable data.

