6 STUDY INTERVENTION(S) OR EXPERIMENTAL MANIPULATION(S)

6.1 STUDY INTERVENTION(S) OR EXPERIMENTAL MANIPULATION(S) ADMINISTRATION

6.1.1 STUDY INTERVENTION OR EXPERIMENTAL MANIPULATION DESCRIPTION

The Companion: Companion is based on Self Determination Theory (SDT) and the application of Motivational Interviewing (MI) to creatively use information on behaviors, attitudes, and environmental contexts to create user-Companion interactions that are tailored to participant needs. SDT addresses cognitive and affective factors in human motivation and posits three innate psychological needs that form the basis for optimal self-motivation: competence, relatedness, and autonomy.³⁰ MI is a client-centered counseling method to explore and resolve uncertainty towards changing behavior and to enhance intrinsic motivation to effect change.³¹ SDT and MI are successfully combined to improve physical activity³² because of a common underlying assumption that people have a tendency for personal growth toward psychological integration.^{33,34}

Next, we describe Companion's technological components, their integration, and integrated function: (1) Continuously worn wireless ActiGraph® wrist sensor capture raw motion data. (2) These data are transmitted hourly to a backend. (3) Motion data are processed immediately at the backend using validated machine learning algorithms to characterize data as physical activity (e.g. walking or other) or sedentary. (4) Processed data are visualized by a health coach using a backend interface that temporally displays estimated behavior types. (5) Research assistants will enquire about major automatically detected behaviors (e.g. movement >10 min; sitting >20 min) to determine context (e.g. walk during lunch; in a weekly meeting) using CS-EMA. (6) They can also choose to determine behavior context of any other automatically detected behavior. (7) These automated and manual records will incrementally yield a reliable visual model of major habitual daily behaviors at the backend. Such information will be richer than what was previously available to an interventionist. (8) Based on the model, coaches will use the CS-EMA two-way communication app to intervene and promote prescription component delivery at opportune times (i.e., near-real-time) to help develop routines.

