Control Group: This group will not receive the Companion, which will be the only difference with the treatment group. I.e., the control group will receive standard treatment– the supervised training program and an exercise prescription for those days when they are on their own. This will be done on the two days when control group participants meet face-to-face with the trainer for supervised training.

Primary Outcomes: Total duration and number of bouts of: (i) light and moderate-to-vigorous physical activity and (ii) sedentary behavior measured over a period of one week using accelerometry.^{38,39} Week-long measures will be made at baseline, and weeks 16 and 24.

Exploratory Outcomes: Cardiometabolic health: Plasma glucose, HbA1C, insulin, and lipids. Body composition: lean and fat mass. Physical function. Muscular and aerobic fitness. Cognition.⁴² Perceptions of competence related to health behaviors. Autonomy support (from companion). Autonomous motivation (for physical activity). Relatedness (to the Companion). General satisfaction.

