(ii) Aerobic Fitness- We will assess aerobic fitness using the 6-minute walk test. This is a simple test that requires no specialized equipment and only requires the participant to walk on a flat, hard surface for a period of 6 min. The total distance walked during this duration is measured using a measuring wheel.

8. Other: (i) 7-14 days after baseline, participants in the general exercise intervention group will have a virtual 30-min face-to-face counseling session with the researchers on: i) benefits of reducing sedentary behavior and increasing physical activity, and ii) various strategies to decrease workplace and home sedentary behaviors and initiate a physically active lifestyle.

(ii) Participants in the lifestyle physical activity intervention group will have a virtual 60-min face-to-face counseling session via a HIPAA complaint ZOOM session. This session will include the same components received by the general exercise intervention group supplemented with an additional 30-min of conversation to further personalize his or her physical activity prescription plan and create goals related to physical activity and sedentary behavior lifestyle choices. During this time the researcher will ask the participant in the lifestyle physical activity intervention group questions about his or her schedule, preferences, health-related behaviors, and other behaviors related to work schedule, hobbies/leisure interests, family dynamics, home and work environment, means of daily transportation, etc. that can be used to help support the participant towards achieving his or her physical activity and sedentary behavior lifestyle goals.

(iii) After study completion, participants will be asked to complete a follow-up interview in person during the end of study follow-up (month 6). The interview will take no longer than 15-20 minutes. The conversations may be recorded only with the participant's permission. Once the audio recordings are transcribed, the audio recordings will be immediately destroyed.

Table 2. Self-completed Measures (1 – 1.5 hours)

Measure	Baseline	Month 4 follow up	Month 6 follow up
General Health and Health Related Quality of Life	✓		
Perceived Competence Scale for Participating in	✓	✓	✓

Regular Physical Activity			
Short Health Care Climate Questionnaire	✓	✓	✓
Exercise Self-Regulation Questionnaire	✓	✓	✓
Basic Need Satisfaction in Relationships Scale	✓	✓	✓
Diet	✓	✓	✓
Activity Monitoring	✓	✓	✓

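### Companion is called the only difference between the arms, but the Companion arm also gets 30 more minutes of live counselling that the plan never assigns to Companion

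*Combined protocol and SAP*

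**What the plan says.** **The claim about the arms.** Section 4.1 says of the control group: "This group will not receive the Companion, which will be the only difference with the treatment group". The Control Group paragraph of 6.1.1 repeats this and describes the control package as "the supervised training program and an exercise prescription for those days when they are on their own". Section 4.2 relies on the contrast: a design in which controls do not receive Companion "will enable to tease apart the efficacy of the Companion".

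**What Companion is.** The synopsis (1.1) says: "The study intervention consists of wearable sensors integrated with the smartphone". The synopsis, 2.2 and 4.1 add a human-in-the-loop approach and tailored text conversations. Section 4.3 gives the delivery mode: "The intervention is delivered via text messaging as it is an mHealth intervention". Section 6.1.1 bases Companion partly on motivational interviewing and then lists its technological components, the last being that "coaches will use the CS-EMA two-way communication app to intervene and promote prescription component delivery at opportune times".

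**What 8.1 item 8 schedules.** Seven to 14 days after baseline, the general exercise group "will have a virtual 30-min face-to-face counseling session with the researchers", covering the benefits of sitting less and moving more and strategies for doing so. The lifestyle physical activity group has a 60-minute session with the same content plus a further half hour. That half hour is used to personalise the prescription, set activity and sedentary-behaviour goals, and ask about schedule, preferences and home and work circumstances.

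**The concern.** If Companion is the only thing that separates the arms, a difference in activity or sedentary time can be credited to Companion, which is how 4.2 reads. Section 8.1 shows a second thing given in unequal amounts: live, one-to-one goal setting on the behaviours that form the primary endpoint. Unless that conversation is part of Companion, the contrast estimates Companion plus extra counselling. What is at stake is the wording of the claim and the reproducibility of the intervention. Someone rebuilding Companion from 1.1, 4.1, 4.3 and 6.1.1 would leave the session out.

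**Working it through.** **Step 1: match the arm names.** Section 8.1 does not use the treatment and control labels for the sessions, so the match is inferred. Under Activity Monitoring in 8.1, only the lifestyle group receives the watch that uploads data passively, and only that group receives 4 to 7 texts a day at intervals of 1 to 4 hours. Section 4.3 gives the same message schedule for Companion. The lifestyle group is therefore the Companion arm and the general exercise group is control.

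**Step 2: the difference in counselling.** From 8.1 item 8: 60 − 30 = 30 min. This reproduces the additional half hour stated there.

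**Step 3: scale.** Supervised exercise (6.1.1) is the same in both arms: twice a week for 16 weeks, about 45 to 60 min each.

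- Sessions: 16 × 2 = 32
- Supervised time: 32 × 45 min = 24 h, up to 32 × 60 min = 32 h
- Control with counselling: 24 + 0.5 = 24.5 h, up to 32 + 0.5 = 32.5 h
- Companion arm with counselling: 24 + 1 = 25 h, up to 32 + 1 = 33 h
- Excess relative to control: 0.5 / 24.5 = 2.0%, down to 0.5 / 32.5 = 1.5%

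This is scheduled session time, not total contact. Monitor exchanges in both arms, hub installation in the Companion arm and the texting itself are left out because their durations are not given.

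**Step 4: is the extra half hour assigned to Companion anywhere?**

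| Section | What it says | Bearing |
|---|---|---|
| 1.1, 2.2, 4.1 | Sensors, smartphone, human-in-the-loop text conversations | No live session named |
| 4.3 | Text messaging is the delivery mode | Points away from a live session |
| 6.1.1, Companion | Motivational interviewing basis, then a list of technological components | Basis is compatible with counselling; a technology list would not be expected to name a session |
| 6.1.1, Treatment Group | Communication in weeks 1 to 4 gathers motivations, preferences, habits and contexts | Content overlaps the extra half hour; session not mentioned |
| 1.3 | Counselling has its own row at Day 7-14, apart from the interventions row | No difference by arm shown |
| 6.2.1, 6.4 | Fidelity and adherence track training and messaging, not this session | Silent |
| 8.1, Activity Monitoring | Text feedback follows the virtual session | Compatible with intake for Companion; not stated |

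No section assigns the session to Companion, and none expressly excludes it.

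**The case against.** The strongest reply is that the extra half hour is simply intake for Companion. Section 6.1.1 builds Companion on motivational interviewing and says that "MI is a client-centered counseling method to explore and resolve uncertainty towards changing behavior". The questions asked in the added time largely match what 6.1.1 has Companion gather in weeks 1 to 4. The Day 7-14 visit falls in that window if weeks are counted from Day 1, and the texts follow the visit. The component list in 6.1.1 is introduced as technological, so its silence about a conversation is weak evidence that the session lies outside Companion. This reading is plausible and may be what the sponsor intends. It does not remove the point: if it is right, the sole-difference statement is true but the definition of Companion is incomplete, and 4.3, which names only text messaging, needs the addition most.

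A second reply is that the amount is trivial, since both arms already outline goals and a plan after supervised sessions. That stands as to size. It does not settle what the contrast is a contrast of.

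A reader might also infer that the control description contradicts 8.1 because it omits the control arm's own 30-minute session. It does not. The omission is in a summary that 8.1 fills in, and both arms receive that content.

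**Conclusion.** The point holds as an either/or: the sole-difference statement in 4.1 and 6.1.1 is wrong, or the definition of Companion is incomplete. The documents do not show which. As written, a between-arm difference cannot be attributed to Companion as now defined.

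The imbalance is one half hour, 1.5% to 2.0% of scheduled session time. Its effect on the outcomes is probably small and cannot be estimated from the documents. The conclusion rests on the inferred match of arm names in 8.1, which is firm.

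A reader might go further and infer that the trial is confounded or that its result would be invalid. The documents do not support that. The extra session comes with the randomised allocation, so treatment versus control remains a valid randomised comparison, and the 4.1 hypotheses, which are worded that way, can still be tested. Nor do the documents support a claim that the extra counselling would account for a material share of any effect.

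**What to change.** Reconcile 4.1, 4.2, 4.3 and 6.1.1 with 8.1 item 8 by stating whether the extended session is part of Companion.

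- **If it is:** add it to the definition in 1.1, 2.2, 4.1, 4.3 and 6.1.1. The primary objective and 4.2 can stand, and the reported conclusion refers to Companion so defined.
- **If it is not:** remove the sole-difference statement from 4.1 and 6.1.1 and list the session as a second between-arm difference. Word the primary objective (1.1 and section 3), 4.2, the 9.1 hypothesis and the reported conclusion as the effect of Companion plus extended counselling.

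In either case, as a minor accompanying edit, name the control arm's 30-minute session in the control descriptions in 4.1 and 6.1.1.

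The cost is a text amendment, recorded under 10.4 as a new approved version. Sessions, sample size and analysis do not change. In the second case there is one further price: a slightly narrower attribution claim.

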4.2 SCIENTIFIC RATIONALE FOR STUDY DESIGN

An RCT design where the control group does not receive the Companion intervention will enable to tease apart the efficacy of the Companion. The design will minimize the risk of confounding and help to increase confidence in the findings, and thus, are more likely to be representative of the true effect of the intervention.

